#### 6.2.8 Early Termination Assessments

Early Termination (ET) assessments of physical examinations, vital signs, [REDACTED] hematology, clinical chemistry, urinalysis will be summarized with the nearest scheduled visit. If the visit already has data, then the result will be binned toward the next scheduled visit.

Methods for analyzing ET assessments of PET imaging data will be detailed in a separate analysis plan, written by [REDACTED]

|  |
|--|
| Confidentiality Statement   |
| This document is the property of [REDACTED] and may not be duplicated, copied, altered or removed from company without prior approval from [REDACTED] or in compliance with [REDACTED] |

|  |  |                  |                         |
|--|--|------------------|-------------------------|
|  |  | Sponsor:         | Pliant Therapeutics Inc |
|  |  | Protocol Number: | PLN-74809-IPF-201       |
| STATISTICAL ANALYSIS PLAN – PHASE 1 |  |                  |                         |

## 6.2.9 Duration / Study Period / Study Day / Time

Study day within each dosing period will be calculated as the number of days from the dose of study drug within the given dosing period.

For events on or after the dose of study drug within the given dosing period:

- Study day = date of event – date of first dose of study drug + 1.

For events before the dose of study drug within the given dosing period:

- Study day = date of event – date of first dose of study drug.

Study day should always be presented in listings along with the dosing period it is relative to (ie “Period X Day X”).

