3 INVESTIGATIONAL PLAN

3.1 Overall Study Design and Plan

| This study is an open-label study in which up to 12 participant | ts with IPF will receive up to |
|---|----------------------------------|
| two doses of PLN-74809, starting at 60 mg | or 80 mg |
| Higher planned doses, including 120 mg, 240 mg | g, and 320 mg, will also be |
| evaluated | |
| All participants will undergo PET imagi | ing at the Baseline Visit and or |
| the day of PLN-74809 dosing. | |

Eligible participants consenting to receive a maximum of 4 different doses of PLN-74809 (e.g., 60 mg and 120 mg) will need to undergo a ≥14-day washout between doses, and not have to repeat Baseline PET imaging. Additionally, if in the opinion of the Investigator, there is no clinical decline, the other Screening and Baseline procedures do not have to be repeated. If the PET ligand cannot be successfully synthetized on the scheduled day, participants will wait at least 1 week before another dose of PLN-74809 is administered.

All PET imaging will be performed using the R_01 Knottin tracer, as generated by the radiology department at Stanford Medical Center. Post-dose PET imaging, for the assessment of $\alpha_v \beta_6$ receptor occupancy, will be performed to coincide with PLN-74809 time to maximum observed drug concentration (T_{max} ; ~4 hours after the administration of study drug). Participants will undergo no more than 3 PET imaging scans (Baseline and up to 2 scans post PLN-74809 dosing).

Blood samples for PLN-74809 PK will be obtained before and at 0.5, 1, 2, 3, and 4 hours after dosing on Day 1 and at 24 hours after dosing (Day 2).

[figure not shown]
Forced vital capacity (FVC) will be performed on all participants at Screening for inclusion/exclusion purposes.

Except for the previously described periods, participants will be allowed to return to their homes between study visits.

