## 1 INTRODUCTION

This document details the planned statistical analyses for Pliant Therapeutics Inc's study PLN-74809-IPF-201, titled "A Phase 2a evaluation of PLN-74809 on  $\alpha_v\beta_6$  receptor occupancy using PET imaging in participants with IPF".

Analyses of the positron emission tomography (PET) imaging data will be detailed in a separate analysis plan, written by [REDACTED]

The proposed analyses are based on the contents of the amended version of the protocol (version 6.0, dated 26 Oct 2021).

This is an open-label study in which up to 12 participants with idiopathic pulmonary fibrosis (IPF) will receive up to 2 doses of PLN-74809, starting at 60 mg [REDACTED] or 80 mg [REDACTED]. Higher planned doses, including 120, 240, and 320 mg, will also be evaluated, [REDACTED]

[REDACTED] All participants will undergo PET imaging at baseline and on the day of PLN-74809 dosing.

Eligible participants consenting to receive a maximum of 4 different single doses of PLN-74809 (eg, 60 and 120 mg) will need to undergo a  $\geq 14$ -day washout between doses and will not need to repeat the baseline PET imaging.

|   |  |  |
|---|--|--|
|   |  |  |
| Confidentiality Statement                   |  |  |
| This document is the property of [REDACTED] |  | . and may not be duplicated, copied, altered or removed from company without prior approval from [REDACTED] or in compliance with [REDACTED] |

|  |  |                              |  |
|--|--|------------------------------|--|
|  |  | Sponsor:
Protocol Number: | Pliant Therapeutics Inc
PLN-74809-IPF-201 |
| STATISTICAL ANALYSIS PLAN – PHASE 1 |  |                              |  |

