| This document is the property of [REDACTED] and may not be duplicated, copied, altered or removed from company without prior approval from [REDACTED] or in compliance with [REDACTED] |  |                                  |

|  |  |  |  |  |  |  |
|--|--|--|--|--|--|--|
|  |  |  |  |  |  |  |
|  |  |  |  |  |  |  |
|  |  |  |  |  |  |  |
| STATISTICAL ANALYSIS PLAN – PHASE 1 |  |  |  |  |  |  |

████████████████████; EOT: end of treatment; EOS: end of study; ET: early termination; FVC: forced vital capacity; HRCT: high-resolution computerized tomography; PET: positron emission tomography; PK: pharmacokinetic.

- a In case the PET ligand cannot be successfully synthesized on the scheduled day, participants will wait at least 1 week and then be dosed again for a second attempt at PET synthesis and imaging.
- b Time 0 refers to immediately predose.
- c Complete physical examination at screening and directed physical examination thereafter.
- d A table of blood volumes is provided in Appendix 3 of the protocol (version 6.0, dated 26 Oct 2021).
- e Urinalysis: dipstick followed up by microscopic examination if needed.
- f An HRCT at screening may not be needed if a scan that meets the quality necessary for diagnosis purposes exists. If an HRCT is performed at screening, a second one is not needed during PET. An HRCT during PET may be performed if the screening HRCT is not adequate for the assessment of HRCT-PET relationship.
- g PET to be performed at least 4 hours post-dose and no more than 30 minutes after the 4 hour PK time point.
- h Blood samples for radiotracer PK to be taken 1, 3, 5, 10, 30, and 60 minutes after completion of radiotracer injection for PET-CT. Each collection time point has a +4-minute window. Refer to the Radiology Manual for details of sample collection including definitive information about allowable windows.
- i Dosing to occur in connection to PET synthesis and availability.
- j Day 2 plasma PK sample to be collected 24 hours post-dose.
- ████████████████████
- l Adverse events and concomitant medications to be collected at each visit.

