#### **3.2 Secondary Endpoints**

1. Incidents of Treatment-Emergent Adverse Events (TEAE)
2. Change from baseline in clinical safety laboratory measures
3. Change from baseline in vital signs
4. [REDACTED]

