## 6.2.11 Unscheduled Visits

For table summaries of observed and change from baseline values, only scheduled post-baseline values will be tabulated. Post-baseline repeat / unscheduled assessments will be disregarded.

For shift tables, scheduled post-baseline, repeat post-baseline, and unscheduled post-baseline values will be tabulated, group by study day.

All post-baseline assessments will be listed in the relevant appendices to the CSR.

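### SAP 6.2.9 defines study day within each dosing period but both formulas count from the first dose; separately, the readable by-dose safety tables name only the pre-first-dose baseline

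*SAP*

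**What the plan says.** **Study day.** SAP 6.2.9 opens by defining study day as "the number of days from the dose of study drug within the given dosing period". It adds that "Study day should always be presented in listings along with the dosing period it is relative to", in the form Period X Day X. It then gives two formulas. For events on or after the period's dose, the subtracted term is "date of first dose of study drug + 1". For earlier events, the same first-dose date is subtracted without adding 1.

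**Where study day is used.** SAP 6.2.11 says that for shift tables scheduled, repeat and "unscheduled post-baseline values will be tabulated, group by study day".

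**Repeat dosing.** SAP 1 provides for participants "consenting to receive a maximum of 4 different single doses of PLN-74809". Protocol 3.1 asks for a minimum "14-day washout between doses" and, after a failed ligand synthesis, a wait of at least 1 week before the next dose. The Schedule of Events labels a re-dose after failed synthesis as Day 8, its next-day visit as Day 9 and its follow-up as Day 15.

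**Baseline.** SAP 6.2.3 defines baseline as the last non-missing value before the first dose. SAP 6.2.4 separately defines a dose-specific baseline as the last value before the dose being analysed. SAP 6.11 presents safety by dose received. The laboratory (6.11.2), vital signs (6.11.3) and physical examination (6.11.5) text refers only to baseline. One secondary endpoint in SAP 3.2 is "Change from baseline in clinical safety laboratory measures", and another is the same quantity for vital signs.

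**The concern.** A formula is what gets programmed, and here it disagrees with the definition above it for every period after the first. The disagreement need not stay in the listings, because the shift tables use study day as their grouping variable. If the formula is followed, a given visit has no fixed row: its position depends on how long each participant waited between doses.

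The baseline question affects what two secondary endpoints measure. A by-dose column invites the reader to attribute its contents to that dose. If change is measured from before the first dose, the column for a second or later dose also contains whatever had already changed before that dose was given. The SAP has a definition that would avoid this, but no readable section applies it.

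**Working it through.** **1. Study day**

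Inputs: the definition and formulas in SAP 6.2.9; the minimum gaps of 14 days and 1 week in Protocol 3.1; the 24 h sample and the 7-day follow-up in the Schedule of Events. A 21-day gap is added as an assumption, for illustration.

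Let g be the days from the first dose to the dose of the period, and t the days from that period's dose to the event.

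- Formula as written: g + t + 1 for t ≥ 0, and g + t for t < 0.
- Definition in the lead sentence: t + 1 for t ≥ 0, and t for t < 0.

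The two differ by exactly g, which is zero only in Period 1. For Period 2:

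| Event (t) | Definition | Formula, g = 7 | Formula, g = 14 | Formula, g = 21 (assumed) |
|---|---|---|---|---|
| Day before dose (-1) | Day -1 | Day 6 | Day 13 | Day 20 |
| Dose day (0) | Day 1 | Day 8 | Day 15 | Day 22 |
| 24 h sample (1) | Day 2 | Day 9 | Day 16 | Day 23 |
| Follow-up (7) | Day 8 | Day 15 | Day 22 | Day 29 |

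Three consequences follow.

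- Pre-dose events in a later period can get positive study days.
- At g = 14, the day before dose 2 is 13 days after dose 1. As a Period 1 event it is 13 + 1 = Day 14; as a Period 2 pre-dose event it is Day 13. The first-dose date is subtracted both times.
- Two participants with gaps of 14 and 21 days would have the same 24 h visit in shift-table rows Day 16 and Day 23.

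The affected share is (n - 1)/n of a participant's periods: 1 of 2 with two doses, 3 of 4 with four.

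At g = 7 the formula gives Day 8, 9 and 15, the numbers on the Schedule's re-dose labels. Under 6.2.5 a period ends before the next dose, so a re-dose would open a new period and the same visits would be Period 2 Day 1, 2 and 8. No rule in the SAP links the two labels.

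**2. Baseline**

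Write B1 for the first-dose baseline, Bk for the dose-specific baseline and Y for a value after dose k. Then

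Y - B1 = (Y - Bk) + (Bk - B1).

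The last term arose before dose k, so it cannot be an effect of dose k, yet the by-dose column includes it. Its size cannot be computed from the documents. B1 is at least 7 days old at a re-dose after failed synthesis and at least 14 days old at a new dose level.

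**3. Time points in 6.11.2**

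This section tabulates every time point after the first dose. The Schedule's footnote b says "Time 0 refers to immediately predose". In a later period the time 0 sample is therefore pre-dose, yet it counts as post-baseline on the literal wording. That is 1 of 3 scheduled haematology and chemistry samples (0 h, Day 2, Day 8) and 1 of 2 for urinalysis (0 h, Day 8). SAP 6.11.3 and 6.11.5 refer to time points after dosing and do not have this wording.

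**The case against.** **The study-day point is a slip whose intent is clear.** The lead sentence, both conditions above the formulas and the Period X Day X label all point to the period's own dose, so a careful programmer may read it correctly. This is fair, and it is why the point is a wording error and not a design fault. It does not remove the error. Elsewhere (6.2.3, 6.2.7, 6.2.10.1) the SAP uses first dose to mean the participant's first dose, and the formulas are the operative text. The laboratory and examination sections do describe shift tables by time point, but 6.2.11 groups scheduled values, as well as unscheduled ones, by study day.

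**The baseline omission may only be apparent.** SAP 6.11.4 and all table titles are redacted. The dose-specific baseline (6.2.4) and the end of dosing period (6.2.5) have no visible use, which suggests that hidden text may use them. This stands as a limit on the claim. A reader might infer that the SAP never applies 6.2.4; the documents do not show that.

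**Change from before the first dose is a defensible safety summary**, because it keeps cumulative change visible. This also stands. The difficulty is using it as the only measure under a by-dose heading.

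**A reader might infer that the first-dose baseline is at least 14, 28 and 42 days old at doses 2, 3 and 4.** That is not a minimum. Protocol 3.1 allows a dose 1 week after a failed synthesis and at most two post-dose scans. Two dose levels, each with one failed synthesis, give 7, 7 + 14 = 21 and 21 + 7 = 28 days.

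**Conclusion.** The study-day formulas in SAP 6.2.9 are wrong as written for every period after the first, by exactly the number of days since the first dose. This rests only on the SAP's own definition and on date arithmetic. Whether tables would actually be misgrouped depends on whether the programmer follows the formula or the sentence above it.

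The baseline point holds on the readable text: the by-dose laboratory, vital-sign and examination tables use a term defined as before the first dose, and the dose-specific term is not invoked. It is less certain because of the redactions, and no size can be given for any carried-over change.

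The consequence is limited. Protocol 9.1 states that no hypotheses are tested, enrolment is up to 12, all laboratory data are listed, and the primary PET analysis lies in a separate plan. A reader should not infer that the trial's main conclusion is at risk. What is at stake is whether the by-dose safety tables can be read as labelled.

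**What to change.** - **6.2.9:** in both formulas, subtract the date of the dose given in that dosing period instead of the date of the first dose. State whether a re-dose after failed synthesis opens a new dosing period, and how the Schedule's Day 8, 9 and 15 labels map to Period X Day X. Every period then reads Day -1, 1, 2 and 8 for the four events above.
- **6.11.2, 6.11.3 and 6.11.5:** name the 6.2.4 dose-specific baseline for the by-dose change and shift tables, or confirm that redacted text already does so.
- **6.11.2:** refer to time points after the given dose, not after the first.
- **Cumulative change:** keep change from the first-dose baseline as a listing or supplementary summary. The SAP promises that laboratory data are listed, but does not say that change values are, so this needs stating.
- **Optional tidy-up in 6.11.1:** a treatment-emergent event may start on or after the first dose, but is allocated to a dose received before onset. Wording that covers a dose at or before onset removes the tie.

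The cost is SAP wording and a little programming, with no new data: laboratory, vital-sign and examination values are already scheduled immediately before dosing. If a pre-dose value is missing, an older one becomes the dose-specific baseline and should be flagged. The corrected formula removes the dependence on dose gap, but not the spread from the ±2-day follow-up window.

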## 6.2.10 Conventions for Missing and Partial Dates

All rules explained below for partial / missing dates will be followed unless contradicted by any other data recorded on the electronic Case Report Form (eCRF).

All dates presented in the individual participant listings will be as recorded on the eCRF (ie, not completed as per the below rules).

### *6.2.10.1 Missing / Partial Start / Stop Date of Adverse Events, Medical History and Concomitant Medications*

Missing and partial start dates will be imputed solely for the purpose of determining whether an AE is treatment-emergent, medical history is ongoing at screening, or a medication is concomitant to study drug.

#### **Partial or missing stop date will be imputed as follows:**

If the stop date is completely missing and the event has resolved, or the participant has stopped taking the concomitant medication, the stop date will be imputed as the date of the participant’s last clinic visit in the study.

- If only the year is known, the stop date will be imputed as “31-Dec” of that year or as the date of the participant’s last clinic visit in the study if in the same year.
- If the month and year are known, the stop date will be imputed as the last day of that month unless the stop date corresponds to the same month as the participant’s last clinic

|   |  |                                  |  |
|---|--|----------------------------------|--|
|   |  | Confidentiality Statement |  |
| This document is the property of [REDACTED], and may not be duplicated, copied, altered or removed from company without prior approval from [REDACTED] or in compliance with [REDACTED] |  |                                  |  |

|  |  |                  |                         |
|--|--|------------------|-------------------------|
|  |  | Sponsor:         | Pliant Therapeutics Inc |
|  |  | Protocol Number: | PLN-74809-IPF-201       |
| STATISTICAL ANALYSIS PLAN – PHASE 1 |  |                  |                         |

visit in which case the date of participant's last clinic visit in the study will be used instead.

**Missing start date will be imputed as follows:**

- If the stop date occurs on or after the start of study drug or the event / concomitant medication is ongoing, the start date will be imputed as the date of the first dose of study drug.
- If the stop date occurs before the start of study drug, the start date of the event / concomitant medication will be imputed as the participant's screening date or the stop date of the event / concomitant medication whichever the earlier.

**Partial start date (year present, but month and day missing)**

- If the stop date occurs on or after the start of study drug or the event / concomitant medication is ongoing, and the year is the same as the year of first dosing the start date will be imputed as "01-Jan" of the same year or the date of the first dose of study drug whichever is latest. If the year is different from the year of first dosing "01-Jan" will be used.
- If the stop date occurs before the start of study drug, the start date of the event / concomitant medication will be imputed as the "01-Jan" of the same year.

**Partial start date (month and year present, but day missing)**

- If the stop date occurs on or after the start of study drug or the event / concomitant medication is ongoing, the start date will be imputed as the first day of the same month and year unless this partial start date is in same month as the first dose of study drug in which case the date of first dose of study drug will be used.
- If the stop date occurs before the start of study drug, the start date will be imputed as the first day of the month and year of the partial stop date.

If the start time is missing it will be imputed only in the case where the start date of the concomitant medication / event corresponds to the date of the first dose of study drug. The time will be imputed as the same time as the first dose of study drug. In all other cases the time will not be imputed.

|  |                                  |  |
|--|----------------------------------|--|
|  | Confidentiality Statement |  |
| This document is the property of [REDACTED] and may not be duplicated, copied, altered or removed from company without prior approval from [REDACTED] or in compliance with [REDACTED] |                                  |  |

|  |  |                  |                         |
|--|--|------------------|-------------------------|
|  |  | Sponsor:         | Pliant Therapeutics Inc |
|  |  | Protocol Number: | PLN-74809-IPF-201       |
| STATISTICAL ANALYSIS PLAN – PHASE 1 |  |                  |                         |

## 6.2.11 Unscheduled Visits

For table summaries of observed and change from baseline values, only scheduled post-baseline values will be tabulated. Post-baseline repeat / unscheduled assessments will be disregarded.

For shift tables, scheduled post-baseline, repeat post-baseline, and unscheduled post-baseline values will be tabulated, group by study day.

All post-baseline assessments will be listed in the relevant appendices to the CSR.

## 6.3 Conventions

All clinical data listings, summaries, figures and statistical analyses will be generated using SAS® [REDACTED]. Summaries of the clinical data will be presented by dose or overall.

Continuous variables will be summarized by the number of non-missing observations (n), mean, standard deviation (SD), median, minimum (min) and maximum (max).

Categorical variables will be summarized by presenting the frequency and percent. Percentages will be based on the number of non-missing observations or the participant population, unless otherwise specified. For each variable, all categories will be shown. Zero frequencies (but not the percent) within a category will be presented.

PK data listings, summaries, figures, and statistical analyses will be generated using Phoenix® WinNonlin® [REDACTED] or SAS® [REDACTED]  
[REDACTED].

PK data (concentration-time data and PK parameters) will be summarized by the number of non-missing observations (n), arithmetic mean (mean), SD, median, min, max, coefficient of variation (CV%), geometric mean, and geometric CV%.

### 6.3.1 Dose Labels

Dose labels will be displayed in the tables, figures and listings (TFLs) as follows:

| 60 mg | 80 mg | 120 mg | 240 mg | 320 mg | Overall |
|-------|-------|--------|--------|--------|---------|
|       |       |        |        |        |         |

|  |  |                                  |  |
|--|--|----------------------------------|--|
|  |  | Confidentiality Statement |  |
| This document is the property of [REDACTED] and may not be duplicated, copied, altered or removed from company without prior approval from [REDACTED] or in compliance with [REDACTED] |  |                                  |  |

|  |  |                  |                         |
|--|--|------------------|-------------------------|
|  |  | Sponsor:         | Pliant Therapeutics Inc |
|  |  | Protocol Number: | PLN-74809-IPF-201       |
| STATISTICAL ANALYSIS PLAN – PHASE 1 |  |                  |                         |

